## Appendix 5. Patient Health Questionnaire (PHQ-8)

Protocol ID: \_\_\_\_\_

CENTER:

SUBJECT ID:

DATE OF VISIT:   -    -

dd                      MMM                      yyyy

Visit: \_\_\_\_\_

### PATIENT HEALTH QUESTIONNAIRE (PHQ-8)

(1) NOT DONE      Language administered:  (44) English for USA

| Over the last 2 weeks , how often have you been bothered by the following problems?   | Not at all
(0)        | Several days
(1)      | More than half the days
(2) | Nearly every day
(3)  |
|--|--------------------------|--------------------------|--------------------------------|--------------------------|
| 1. Little interest or pleasure in doing things?  |  |  |        |  |
| 2. Feeling down, depressed, or hopeless?   |  |  |        |  |
| 3. Trouble falling or staying asleep, or sleeping too much?  |  |  |        |  |
| 4. Feeling tired or having little energy?  |  |  |        |  |
| 5. Poor appetite or overeating?  |  |  |        |  |
| 6. Feeling bad about yourself—or that you are a failure or have let yourself or your family down?  |  |  |        |  |
| 7. Trouble concentrating on things, such as reading the newspaper or watching television?  |  |  |        |  |
| 8. Moving or speaking so slowly that other people could have noticed? Or the opposite—being so fidgety or restless that you have been moving around a lot more than usual? |  |  |        |  |

If you are experiencing any of the problems on this form, how difficult have these problems made it for you to do your work, take care of things at home or get along with other people?

|                                |                              |                          |                               |
|--------------------------------|------------------------------|--------------------------|-------------------------------|

## Appendix 6. Neurologic Assessment in Neuro-Oncology (NANO) Scale

Figure 1. Neurologic Assessment in Neuro-Oncology (NANO) Scale

**Scoring assessment is based on direct observation and testing performed during clinical evaluation and is not based on historical information or reported symptoms. Please check 1 answer per domain. Please check “Not assessed” if testing for that domain is not done. Please check “Not evaluable” if a given domain cannot be scored accurately due to pre-existing conditions, co-morbid events and/or concurrent medications.**

Date Assessment Performed (day/month/year): \_\_\_\_\_

Study time point (i.e. baseline, cycle 1, day 1, etc): \_\_\_\_\_

Assessment performed by (please print name): \_\_\_\_\_

### Domains

### Key Considerations

#### Gait

- 0  Normal
- 1  Abnormal but walks without assistance
- 2  Abnormal and requires assistance (companion, cane, walker, etc.)
- 3  Unable to walk
  - Not assessed
  - Not evaluable

- Walking is ideally assessed by at least 10 steps

#### Strength

- 0  Normal
- 1  Movement present but decreased against resistance
- 2  Movement present but none against resistance
- 3  No movement
  - Not assessed
  - Not evaluable

- Test each limb separately
- Recommend assess proximal (above knee or elbow) and distal (below knee or elbow) major muscle groups
- Score should reflect worst performing area
- Patients with baseline level 3 function in one major muscle group/limb can be scored based on assessment of other major muscle groups/limb

#### Ataxia (upper extremity)

- 0  Able to finger to nose touch without difficulty
- 1  Able to finger to nose touch but difficult
- 2  Unable to finger to nose touch
  - Not assessed
  - Not evaluable

- Non-evaluable if strength is compromised
- Trunk/lower extremities assessed by gait domain
- Particularly important for patients with brainstem and cerebellar tumors
- Score based on best response of at least 3 attempts

#### Sensation

- 0  Normal
- 1  Decreased but aware of sensory modality
- 2  Unaware of sensory modality
  - Not assessed
  - Not evaluable

- Recommend evaluating major body areas separately (face, limbs and trunk)
- Score should reflect worst performing area
- Sensory modality includes but not limited to light touch, pinprick, temperature and proprioception
- Patients with baseline level 2 function in one major body area can be scored based on assessment of other major body areas

Visual Fields

- 0  Normal
- 1  Inconsistent or equivocal partial hemianopsia (≥quadrantopsia)
- 2  Consistent or unequivocal partial hemianopsia (≥quadrantopsia)
- 3  Complete hemianopsia
  - Not assessed
  - Not evaluable

- Patients who require corrective lenses should be evaluated while wearing corrective lenses
- Each eye should be evaluated and score should reflect the worst performing eye

Facial Strength

- 0  Normal
- 1  Mild/moderate weakness
- 2  Severe facial weakness
  - Not assessed
  - Not evaluable

- Particularly important for brainstem tumors
- Weakness includes nasolabial fold flattening, asymmetric smile and difficulty elevating eyebrows

Language

- 0  Normal
- 1  Abnormal but easily conveys meaning to examiner
- 2  Abnormal and difficulty conveying meaning to examiner
- 3  Abnormal. If verbal, unable to convey meaning to examiner. OR non-verbal (mute/global aphasia)
  - Not assessed
  - Not evaluable

- Assess based on spoken speech. Non-verbal cues or writing should not be included.
- **Level 1:** Includes word finding difficulty; few paraphasic errors/neologisms/word substitutions; but able to form sentences (full/broken)
- **Level 2:** Includes inability to form sentences (<4 words per phrase/sentence); limited word output; fluent but “empty” speech.

Level of Consciousness

- 0  Normal
- 1  Drowsy (easily arousable)
- 2  Somnolent (difficult to arouse)
- 3  Unarousable/coma
  - Not assessed
  - Not evaluable

- None

Behavior

- 0  Normal
- 1  Mild/moderate alteration
- 2  Severe alteration
  - Not assessed
  - Not evaluable

- Particularly important for frontal lobe tumors
- Alteration includes but is not limited to apathy, disinhibition and confusion
- Consider subclinical seizures for significant alteration

Appendix 1. Appendices		
Appendix 1.1. Summarizing Relative Dose (RD) and Relative Dose Intensity (RDI)	

Amendment 1	Section 2.1 and	Wording for sample size was updated to be
	4.3	consistent with the protocol amendment.
	Section 8.2.4.2	Shift table for ECG abnormality was deemed
		unnecessary in this study and was removed.
	Section 8.2.4.2	A brief paragraph about ECHO/MUGA data was
		added.
	Section 8.2.9.1	Further details about neurologic and cognitive
		assessment data (HVLT-R, TMT, COWA,
		NANO) were added.
		Other editorial updates to be consistent with the
		protocol amendment.

1. AMENDMENTS FROM PREVIOUS VERSION(S)

2. INTRODUCTION

This document presents the statistical analysis plan (SAP) for study C0591001. The SAP is based on the protocol amendment 1 for C0591001 dated December 19, 2016.

Note: in this document any text taken directly from the protocol is *italicized*.

2.1. Study Design

This is a Phase 1, open-label, multi-center, multiple-dose, safety, PK and PD study of single agent PF-06840003. This study contains two parts, dose escalation (Part 1) followed by dose expansion (Part 2). In Part 1, sequential cohorts of patients with recurrent malignant gliomas (GBM and/or WHO grade III gliomas) will receive escalating doses of PF-06840003. Part 2 will evaluate safety as well as explore preliminary antitumor activity of the dose selected from Part 1 in additional patients with GBM.

The actual number of patients enrolled in the study will depend on the tolerability of *PF-06840003* and the number of dose levels required to identify the MTD or Recommended Phase 2 Dose (RP2D) if the MTD is not reached. The target sample size for each cohort in Part 1 is 2-4 patients, but, the actual number of patients treated at each dose will vary from 2 to 12. It is estimated that the maximum sample size will be approximately 72 patients in Part 1 of the study, although this may be higher if more than 6 dose levels are required to be evaluated. Up to approximately 20 to 25 patients are anticipated to be enrolled in Part 2 of the study.

The overall study design is depicted in Figure 1.

Figure 1. Overall Study Design

2.2. Study Objectives

Primary Objective – Part 1

- To evaluate the safety and tolerability of increasing dose levels of daily oral *PF-6840003* in patients with malignant gliomas.
- To characterize the dose limiting toxicities (DLTs) of escalated doses of *PF-06840003*.
- To determine the maximum tolerated dose (MTD) or recommended phase 2 dose (RP2D).

Primary Objective – Part 2

- To further evaluate the safety and tolerability of PF-06840003 at the RP2D.
- To evaluate the efficacy of PF-06840003 in patients with glioblastoma.

Secondary Objectives Parts 1 and 2

- To evaluate the overall safety profile.
- To characterize the single and multiple dose plasma PK of active enantiomer *PF-06840002*, and inactive enantiomer *PF-06840001* after administration of the racemic mixture, *PF-06840003*.

- To document any anti-tumor activity (Part 1 only).
- To evaluate dose and concentration response relationship for target engagement and PD biomarkers and to then correlate with PK, safety and efficacy to select dose with full or optimal target engagement.
- To assess the CSF PK exposure of active enantiomer PF-06840002, and inactive enantiomer PF-06840001 after administration of the racemic mixture, PF-06840003.

3. INTERIM ANALYSES, FINAL ANALYSES AND UNBLINDING

There is no formal interim analysis planned in this study. This is an open label study, the Pfizer study team will review safety, immunogenicity, pharmacodynamics, CCI and other data throughout the study.

4. HYPOTHESES, SAMPLE SIZE AND DECISION RULES

4.1. Statistical Hypotheses

There are no statistical hypotheses in this study.

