#### **9.4. Efficacy Analysis**

There is no efficacy analysis in the dose escalation phase of the study (Part 1).

In the expansion phase (Part 2), anti-tumor activity is one of the two primary objectives.

Tumor assessment in the study will be based on the Macdonald criteria. DCR, ORR, duration of response (DOR), and Progression-Free Survival (PFS) will be calculated and presented. For binary variable (eg, ORR, DCR), descriptive statistics will be used; for time-to-event variables (eg, DOR, PFS), Kaplan-Meier analysis may be performed. The detailed analyses will be described in the statistical analysis plan.

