4.3. Sample Size Determination

Due to the dynamic nature of the Bayesian allocation procedure, the sample size using the mTPI approach cannot be determined in advance in the dose escalation phase of the study. The target sample size for each cohort is 2 to 4, the actual number of patients treated at each dose will vary from 2 to 12. It is estimated that the maximum sample size will be approximately 72 patients in Part 1 of the study, although this may be higher if more than 6 dose levels are required to be evaluated. Up to approximately 20 to 25 patients are anticipated to be enrolled in Part 2 of the study.

In Part 2, the expansion phase of the study, multiple efficacy endpoints will be investigated, namely: 1) disease control rate (DCR) at Week 9; 2) DCR at Week 25; 3) objective response rate (ORR) by MRI by or at Week 9; 4) ORR by F-18-FLT-PET scan by or at Week 9 (if collected). The sample size is driven by DCR at Week 9 and ORR by MRI.

The expansion phase of the study will be a single arm study, the recommended dose from Part 1 will be used in this phase. With 20 patients, the study will have an approximately 75% power to detect a 25% improvement in Disease Control Rate (DCR), aiming for a 65% DCR, from the null hypothesis of 40% DCR. The study will have an approximately 78% power to detect a 15% improvement in ORR, aiming for a 20% ORR, from the null hypothesis of 5% ORR. These sample size calculations use a one-sample test for a single

proportion with a one-sided alpha level of 0.05. The statistical power will be slightly higher than stated above if this phase of the study enrolls more than 20-25 patients.

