8.2.5.1. Primary Efficacy Analysis

Tumor assessments including MRI will be performed every 8 weeks (with an allowable window per study protocol) after the first dose. Disease control rate (DCR), defined as the proportion of patients achieving CR, PR, or SD as assessed by Macdonald criteria, will be summarized and listed by dose level and week. A cycle is 4 weeks long. Number of weeks will be derived based on cycle numbers. This will be performed for Part 1 and Part 2 separately. If deemed necessary and data permits, a combined analysis may be performed where Part 2 and the same dose level in Part 1 as that in Part 2 will be combined. These analyses will be based on investigator provided overall disease assessment.

As data accumulates, a Bayesian approach with a non-informative Jeffery's prior beta (0.5, 0.5) will be used to calculate the posterior probability of observing certain DCR (eg, 40%, 50%, 60% etc.). The purpose of it is to monitor data on an ongoing basis and to provide more analytical data for the study team. No official analysis output needs to be generated for this. This is only applicable to Part 2.

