Progress-free survival (PFS) is defined as the time from date of enrollment to first PD or death due to any cause in the absence of documented PD. PFS will be analyzed in an exploratory manner. Kaplan-Meier analysis may be performed. If it is performed, the median PFS and 2-sided 95% confidence interval will be reported by dose level. Kaplan-Meier plot may also be generated by dose level.

This will be performed for Part 1 and Part 2 separately. If deemed necessary and data permits, a combined analysis may be performed where Part 2 and the same dose level in Part 1 as that in Part 2 will be combined.

Tumor measurement and assessment data

Tumor measurement data (target lesions, new measurable lesions, non-target lesions, and new non-measurable lesions), as collected, will be listed at patient level by dose and cycle.

Tumor assessment data for both Macdonald criteria and RANO criteria will be listed at patient level by dose and cycle.

Summary table for this data may be generated, if deemed necessary.

CCI		
CCI		

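### SAP 4.1 denies any hypotheses, yet Part 2 is sized on null hypotheses for DCR and ORR, and the plan specifies no final test, success criterion or interval for either

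*SAP*

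**What the plan says.** SAP 4.1 reads, in full, "There are no statistical hypotheses in this study".

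SAP 4.3, matching Protocol 9.3, sizes Part 2 on hypotheses. For DCR it is "aiming for a 65% DCR, from the null hypothesis of 40% DCR"; for ORR, "aiming for a 20% ORR, from the null hypothesis of 5% ORR". Both use a one-sample test of a proportion at one-sided alpha 0.05 with 20 patients, and the stated power is about 75% and 78%. The same sections say that Week 9 DCR and ORR by MRI drive the sample size.

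Efficacy in glioblastoma is a primary objective of Part 2 (SAP 2.2). Macdonald DCR at Weeks 9 and 25 is a primary endpoint (SAP 6.2), and ORR is secondary (SAP 6.3).

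For the analysis, Protocol 9.4 says "For binary variable (eg, ORR, DCR), descriptive statistics will be used" and leaves the detail to the SAP. SAP 8.2.5.1 says that DCR "will be summarized and listed by dose level and week", and SAP 8.2.5.2 treats ORR in nearly the same way. SAP 8 gives counts and percentages for categorical data in general.

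Both efficacy subsections also describe posterior probabilities under a beta(0.5, 0.5) prior, for ongoing monitoring and without official output. Protocol 9.3 and SAP 8.2.5.2 allow a futility stop if the posterior probability is below 15% for both endpoints. The only efficacy interval in the readable text is for progression-free survival: "the median PFS and 2-sided 95% confidence interval will be reported by dose level". That analysis is exploratory and done only if Kaplan-Meier is performed.

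**The concern.** The two SAP sections cannot both stand: a power statement needs a null hypothesis and a test, and 4.1 says there is no hypothesis. The analysis sections follow 4.1, so the quoted power describes a test that nobody is committed to run.

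What is at stake is how a primary objective is read. Part 2 is single-arm and open-label, with about 20 patients, and the study team sees data throughout (SAP 3). With no named method, confidence level or threshold, a result near the boundary can be described as better than 40%, or as not distinguishable from 40%, according to a choice made after the counts are known.

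**Working it through.** **Inputs** (SAP 4.3, Protocol 9.3): n = 20; DCR p0 = 0.40, p1 = 0.65; ORR p0 = 0.05, p1 = 0.20; one-sided alpha 0.05 (z = 1.645). No dropout rate is stated for Part 2, so none is applied.

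**Step 1: reproduce the stated power.** Normal approximation without continuity correction:

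power = Φ[(p1 − p0 − 1.645·s0) / s1], with s0 = √(p0(1−p0)/n) and s1 = √(p1(1−p1)/n).

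- DCR: s0 = √(0.40×0.60/20) = 0.1095; s1 = √(0.65×0.35/20) = 0.1067. (0.25 − 0.1802)/0.1067 = 0.654, so power is 74.4% (stated: about 75%).
- ORR: s0 = √(0.05×0.95/20) = 0.0487; s1 = √(0.20×0.80/20) = 0.0894. (0.15 − 0.0802)/0.0894 = 0.781, so power is 78.3% (stated: about 78%).

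Both figures reproduce.

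**Step 2: what that test would decide.** With z = (x/n − p0)/s0:

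- DCR 12/20: (0.60 − 0.40)/0.1095 = 1.83, above 1.645.
- ORR 3/20: (0.15 − 0.05)/0.0487 = 2.05, above 1.645.

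The approximate test rejects at both counts.

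**Step 3: the same counts under other standard methods.** Clopper-Pearson 90% limits are the 5% quantile of beta(x, n−x+1) and the 95% quantile of beta(x+1, n−x). Jeffreys 90% limits are the 5% and 95% quantiles of beta(x+0.5, n−x+0.5).

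| Result | Null | Exact 90% CI | Jeffreys 90% interval |
|---|---|---|---|
| DCR 12/20 | 40% | 39.4% to 78.3% (includes null) | 41.8% to 76.2% (excludes) |
| DCR 13/20 | 40% | 44.2% to 82.3% (excludes) | not needed |
| ORR 3/20 | 5% | 4.2% to 34.4% (includes null) | 5.6% to 31.4% (excludes) |
| ORR 4/20 | 5% | 7.1% to 40.1% (excludes) | not needed |

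At 12/20 and 3/20 the answer depends on the method.

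**Step 4: exact error rates of each cut-off.** Alpha = P(X ≥ r | n, p0) and power = P(X ≥ r | n, p1), both binomial.

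| Rule | True one-sided alpha | Power |
|---|---|---|
| DCR ≥ 12/20 | 5.7% | 76.2% |
| DCR ≥ 13/20 | 2.1% | 60.1% |
| ORR ≥ 3/20 | 7.5% | 79.4% |
| ORR ≥ 4/20 | 1.6% | 58.9% |

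The cut-offs that give roughly the stated power exceed the stated alpha. Those that respect alpha have about 60% and 59% power. At n = 25 the position is better: ≥ 15/25 for DCR has alpha 3.4% and power 77.1%; ≥ 4/25 for ORR has alpha 3.4% and power 76.6%.

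**The case against.** The strongest reply is that this is a Phase 1 study whose Part 2 explores preliminary activity, so description is enough and any reader can compute an interval from x/20. That would justify keeping 4.1, but not keeping the power statement beside it. Nor does it replace a pre-specified method, since Step 3 shows that the reader's choice of interval matters.

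A second reply is that the plan does contain inference. This is partly right. A reader might infer that the plan has no inferential calculation or cut-off at all, or that the trial could not say whether DCR exceeds 40%. The documents do not support that. SAP 8.2.5.1 gives 40% as an example value for the posterior calculation, and at 12/20 the Jeffreys posterior probability that DCR exceeds 40% is 96.5%. There is also the 15% futility threshold. What is missing is a success threshold and a reported final inference.

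A third reply is that calling 12/20 or 3/20 inconclusive merely reflects a conservative interval. This stands. The approximate test behind the power, and intervals under the plan's own prior, exclude the nulls. These examples show dependence on an unspecified method, not that the plan itself makes such results inconclusive.

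Finally, parts of SAP 8.2.5.2 and later sections are redacted, so the statement about intervals is limited to readable text. The DCR and ORR analysis paragraphs are readable.

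**Conclusion.** The concern holds in this form: SAP 4.1 contradicts SAP 4.3 and Protocol 9.3, and the readable plan gives no final test, success criterion or interval for DCR or ORR. The stated power therefore belongs to no planned analysis.

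The size is one patient either way at n = 20. Conclusions at 12/20 (DCR) and 3/20 (ORR) turn on the method; at 13/20 and 4/20 even the exact interval excludes the null. If the test were run exactly within alpha 0.05, power would be about 60% and 59%, not 75% and 78%.

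A reader might infer that the power figures are miscalculated. They are not: they are right for the uncorrected normal approximation. The 78% also belongs to ORR, a secondary endpoint, and not to the primary DCR.

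The n = 20 figures assume that all 20 patients count in the denominator; the cut-offs shift with the final number, as the n = 25 figures show. The documents give no separate null for Week 25 DCR, so none of this extends to it.

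**What to change.** In SAP 8.2.5.1 and 8.2.5.2, report exact (Clopper-Pearson) two-sided 90% confidence intervals for Part 2 DCR and ORR in the full analysis set, which SAP 5.2 already assigns to efficacy. Week 25 DCR gets an interval only. Then reconcile 4.1 with 4.3 in one of two ways.

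(a) **Keep the hypotheses.** State in 4.1 that Week 9 DCR is tested against 40%, with ORR against 5% as supportive. Claim improvement over the null only if the lower 90% limit exceeds 40% (or 5%), which at n = 20 means at least 13/20 (or 4/20). Restate power at n = 20, in SAP 4.3 and Protocol 9.3, as about 60% for DCR (true alpha 2.1%) and 59% for ORR (true alpha 1.6%). Adding the exact rule while leaving 75% and 78% in place would recreate the mismatch. Tie the cut-offs to the final number analysed.

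(b) **Keep 4.1.** Delete the power statement from both documents and justify 20 to 25 patients by precision. At an observed 60%, for example, the exact 90% interval runs from 39.4% to 78.3% at 12/20 (78.3 − 39.4 = 38.9 points wide) and from 41.7% to 76.4% at 15/25 (76.4 − 41.7 = 34.7 points wide).

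The cost is SAP text, a few lines of output and a matching change to Protocol 9.3. Section 9 of the protocol requires an amendment for major changes to the primary endpoint analysis, so option (a) should be checked against that. Data collection and patient management do not change. The downside is a more guarded claim and, under (a), a less favourable stated power.

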4.2. Statistical Decision Rules

In Part 1 of the study, dose escalation and de-escalation will follow a modified Toxicity Probability Interval (mTPI) method, targeting a DLT rate of 27.5% and an acceptable DLT interval 22.5 to 32.5%. The mTPI method relies upon a statistical probability algorithm, calculated using all patients treated in the current dose level to determine one of the following dose-finding decisions: the subsequent dose should be escalated, maintained at the current dose, or de-escalated in the next cohort of 2 to 4 patients, or the trial should be terminated.

As an example, if the total number of patients treated at the current dose level is 4, the following dosing rules are applied:

- 0 DLT -> escalate;
- 1 DLT -> remain at the same dose;
- 2 DLTs -> de-escalate;
- *3-4 DLTs -> de-escalate and consider current dose as intolerable.*

The general approach to dose-finding, using the mTPI method, involves the following:

- The target cohort size is 2 to 4, depending on the number of potential patients identified at participating sites;
- The next cohort can be enrolled when all patients at the current dose cohort have been evaluated for 28 days of the first treatment cycle, or experience a dose-limiting toxicity (DLT), whichever comes first;
- If a patient withdraws from the study before receiving ≥80% of the planned first-cycle dose for reasons other than investigational product-related toxicity, another patient will be enrolled to replace that patient at the current dose combination;
- In the situation in which the safety of the starting dose does not allow for escalation to the next dose level, a lower dose will be considered.

The dose escalation portion of the study is completed when at least 6 to 12 evaluable patients have been treated at the highest dose associated with DLT rate $\leq 32.5\%$.

Number of Patients	Number of Patients Treated at a Dose Level										
having DLT	n=2	n=3	n=4	n=5	n=6	n=7	n=8	n=9	n=10	n=11	n=12
0	Е	Е	Е	Е	Е	Е	Е	Е	Е	Е	Е
1	S	S	S	Е	E	Е	E	Е	E	Е	Е
2	U	D	S	S	S	S	S	S	S	Е	Е
3		U	U	D	D	S	S	S	S	S	S
4			U	U	U	U	D	D	D	S	S
5				U	U	U	U	U	D	D	D
6					U	U	U	U	U	Ū	U
7						U	U	U	U	U	U

Table 1.Decision Rules

Actions to be taken:

D = De-escalate the dose; E: Escalate the dose; S: Stay at the dose.

U = Unacceptable toxicity.

